## 9. University of Rochester [UR] Site Administration

The Wilmot Cancer Institute, Clinical Trials Office at the University of Rochester will serve as the Coordinating Center for this multi-site study. The lead PI of the Coordinating Center is affiliated with the UR and is also the UR enrolling site PI. Both the lead PI and Coordinating Center will assume responsibility for the overall conduct and management of the study, including the following responsibilities:

- Ensure all approval of protocol documents, including model consent forms are distributed to enrolling sites and approved by enrolling site IRBs prior to implementation.
- Maintain a regulatory file for the Coordinating Center and for each enrolling site.
- Monitor subject enrollment and participation.
- Ensure informed consent is obtained from each subject and consent is in compliance with federal, state and local regulations, as well as the study protocol.
- Ensure compliance with the study protocol (including timely reporting of all research events) and data validity and integrity.
- Convey study-related information to enrolling sites, sponsors and study-specific committees, as needed.
- Respond to enrolling site protocol inquires and questions.
- Provide enrolling site staff continued training on the conduct of the study, as necessary.
- Ensure all enrolling sites are notified when enrollment is complete, and all study-related activities are complete.
- Verify each enrolling site closed the study with their IRB.
- Ensure the data set and any stored samples are appropriately de-identified or coded and managed per the study protocol.

### **Distribution of Study Documents to Enrolling Sites and Obtaining Enrolling Site IRB Approval**

Protocol documents (submitted both at the time of initial approval and via amendment) should be submitted and approved by the Coordinating Center's IRB prior to distribution to enrolling sites. Once enrolling sites receive the study documents, they then must submit applications to their respective IRB for approval prior to initiation of the study at their site.

Any changes to protocol documents requested by the enrolling site and/or their IRB should be reviewed and approved by the Coordinating Center prior to re-submission to the enrolling site's IRB. Any substantive changes to study documents by the enrolling site should be appropriately justified. Every effort should be made to avoid changing the protocol for individual enrolling sites; however, in certain circumstances it may be appropriate for sites to include site-specific addendums in order to comply with their institution's policies and procedures. Editorial changes to the consent form are also generally permissible as long as they do not change the content or intent of the document.

Once the study and/or amendment has been approved by the enrolling site IRB, a copy of the approval notification and all related approved study documents must be provided to the Coordinating Center prior to initiation of the study at the enrolling site.

### **Study Monitoring & Auditing**

All aspects of the study will be monitored closely by the site PI's, the Coordinating Center and the Sponsor. Monitoring will be conducted according to GCP and standard operating procedures for compliance with applicable government regulations. As a participating site, the Investigator grants permission to the Coordinating Center and/or appropriate regulatory authorities to conduct routine remote monitoring and/or on-site monitoring of all appropriate study documentation if requested.

Inspections by regulatory health authority representatives i.e. FDA and IEC(s)/IRB(s) can occur at any time during or after completion of the study. The investigator should notify the Coordinating Center immediately of any such inspection.

Documentation of monitoring will be maintained by the Coordinating Center.

### **Essential Study Documentation**

The Coordinating Center will be responsible for maintaining essential documentation for the Coordinating Center as well as for the enrolling sites. These essential documents permit the conduct of the study and demonstrate compliance with the protocol and regulatory requirements. Copies of all regulatory documents from each enrolling site should be scanned and emailed to: [[name]\\[contact]](mailto:[contact]). The regulatory team at the Coordinating Center will track and monitor these documents.

Examples of these documents include but are not limited to:

- Dated IRB approval notifications for site protocols, informed consent forms, recruitment materials, and case report forms (including initial approvals, amendments and progress reports); include all approved versions;
- Signed clinical trial agreements between all involved parties;
- Signed and dated CVs;

- Investigational product label samples, handling instructions, shipping records and accountability records;
- All versions of the Investigator’s Brochure, if applicable;
- Monitoring reports; and
- Reportable research events.

Essential documents shall be archived safely and securely in such a way that ensures that they are readily available upon authorities’ request.

Patient (hospital) files will be archived according to local regulations and in accordance with the maximum period of time permitted by the hospital, institution or private practice.

### **Drug logistics and accountability**

The drug will be shipped directly to the Investigational Pharmacy at the Coordinating Center, which will in turn dispense the medication to the other enrolling sites.

All study drugs will be stored at the investigational site in accordance with Good Clinical Practice (GCP) and Good Manufacturing Practices (GMP) requirements and the instructions given by the clinical supplies department of the Institution and will be inaccessible to unauthorized personnel.

#### **Accountability**

The investigator at each site or a responsible party designated by the investigator must maintain a careful record of the inventory and disposition of the agent, including dates and lot numbers of all study drug received. All study drug supplies issued to, used by, and returned by each patient must be recorded using the NCI Drug Accountability Record or another comparable drug accountability form. (See the CTEP website at <http://ctep.cancer.gov/protocolDevelopment> for the “Policy and Guidelines for Accountability and Storage of Investigational Agents” or to obtain a copy of the drug accountability form.)

#### **Destruction and Return**

At the end of the study, unused supplies of Regorafenib, opened or unopened should be destroyed according to institutional policies in accordance with the requirements outlined in the study contract ONLY after study drug accountability has been completed and with approval of the study PI. Destruction will be documented in the Drug Accountability Record Form. The certificate of destruction should be sent to the Coordinating Center.

A completed “Unused Study Drug Disposition Form Destruction or Return Confirmation” should be sent to the Coordinating Center. The Coordinating Center will ensure all forms from sites are sent to Bayer at the following address:

**Subject information and consent**

Patients must be informed of the investigational nature of this study and must sign and give written informed consent in accordance with institutional and federal guidelines. Voluntary written informed consent must be obtained before registration or performance of any study-related procedure not part of normal medical care.

Each subject will have ample time and opportunity to ask questions and will be informed about the right to withdraw from the study at any time without any disadvantage and without having to provide reasons for this decision.

Only if the subject voluntarily agrees to sign the informed consent form and has done so, may he/she enter the study. Additionally, the investigator and other information provider (if any) will personally sign and date the form. The subject will receive a copy of the signed and dated form.

The signed informed consent statement is to remain in the investigator site file or, if locally required, in the patient's note/file of the medical institution.

In the event that informed consent is obtained on the date that baseline study procedures are performed, the study record or subject's clinical record must clearly show that informed consent was obtained prior to these procedures.

The informed consent form and any other written information provided to subjects will be revised whenever important new information becomes available that may be relevant to the subject's consent, or there is an amendment to the protocol that necessitates a change to the content of the subject information and / or the written informed consent form.

The Coordinating Center will first approve consent form/amendment changes through their IRB and once approved, will distribute to enrolling sites. Once these changes have been approved by the enrolling site IRB, a copy of the approval notification and all related approved study documents must be provided to the Coordinating Center prior to use. The investigator will inform the subject of changes in a timely manner and will ask the subject to confirm his/her participation in the study by signing the revised informed consent form.

### **Registration and Data handling**

All patients will be registered through the Coordinating site, Clinical Trials Office, which is located at the:

James P. Wilmot Cancer Institute  
University of Rochester Medical Center  
[name]

Each site will receive access to the study-specific, REDCap database at the University of Rochester.

It is the expectation that all data has source documentation available at the enrolling sites. Site personnel will be responsible for entering their patient data regularly into this database.

At the time of registration, the signed informed consent form and documents that support eligibility should be emailed in pdf format to the data manager, [name], at the Coordinating Center: [[name]\\[contact]](mailto:[contact]).

The signed consent form and supporting documents can also be faxed to the Coordinating Center at [contact]. Please inform the data manager by email that the eligibility forms have been faxed.

Any question regarding eligibility or that may arise during the conduct of the study should be addressed to:

Name: [name]  
Email: [[name]\\[contact]](mailto:[contact])  
[contact]

### **10. Treatment compliance**

Subject compliance with the treatment and protocol includes willingness to comply with all aspects of the protocol, and to have blood collected for all safety evaluations. At the discretion of the principal investigator, a subject may be discontinued from the trial for non-compliance with follow-up visits or study drug.

### **Prior and concomitant therapy**

All medication that is considered necessary for the subject's welfare may be given at the discretion of the investigator. All medications (including contrast media) taken within 2 weeks

prior to the start of the study and during the study must be recorded in the subject's source documentation and in the CRF (including start/stop dates, dose frequency, route of administration, and indication). Specific caution should be taken when considering or administering a concomitant medication that is metabolized by the cytochrome enzymes CYP2C8, CYP2B6 and CYP2C9. Such concomitant medication should be avoided, if possible.

Co-administration of a strong CYP3A4 inducer (rifampin) with a single 160 mg dose of regorafenib decreased the mean exposure of regorafenib, increased the mean exposure of the active metabolite M-5, and resulted in no change in the mean exposure of the active metabolite M-2. Avoid concomitant use of regorafenib with strong CYP3A4 inducers (e.g. rifampin, phenytoin, carbamazepine, phenobarbital, and St. John's Wort).

Co administration of a strong CYP3A4 inhibitor (ketoconazole) with a single 160mg dose of regorafenib increased the mean exposure of regorafenib and decreased the mean exposure of the active metabolites M-2 and M-5. Avoid concomitant use of regorafenib with strong inhibitors of CYP3A4 activity (e.g. clarithromycin, grapefruit juice, itraconazole, ketoconazole, nefazadone, posaconazole, telithromycin, and voriconazole).

Permitted concomitant therapy includes:

- Standard therapies for concurrent medical conditions.
- Supportive care for any underlying illness.
- Palliative radiation therapy is allowed if the target lesion(s) are not included within the radiation field and no more than 10% of the bone marrow is irradiated.
- Granulocyte colony-stimulating factor (G-CSF) and other hematopoietic growth factors may be used in the management of acute toxicity, such as febrile neutropenia, when clinically indicated or at the investigator's discretion. However, they may not be substituted for a required dose reduction. Subjects are permitted to take chronic erythropoietin.
- Treatment with nonconventional therapies (such as acupuncture), and vitamin/mineral supplements are permitted provided that they do not interfere with the study endpoints, in the opinion of the investigator.
- Bisphosphonates

The following are not permitted:

- Other investigational treatment during or within 28 days before starting study treatment
- Systemic antitumor therapy, including cytotoxic therapy, signal transduction inhibitors, immunotherapy, and hormonal therapy for colorectal cancer
- Bone marrow transplant or stem cell rescue
- Subjects taking narrow therapeutic index medications should be monitored proactively (e.g. phenytoin, quinidine, carbamazepine, Phenobarbital, cyclosporin, and digoxin).

- Liver function tests should be obtained before initiation of regorafenib and monitored at least every 2 weeks during first 2 months of treatment. Thereafter liver function should be monitored monthly or more frequently as clinically indicated

## Follow-up Period

### Follow-up Prior to Progression

- Patients who come off treatment for reasons other than progression of disease will have physical exams performed at least every 3 months or earlier as clinically indicated until the follow-up period is terminated (see Reasons for Follow-up Termination). Frequency of radiographic studies will be at the discretion of the treating physicians.
- After disease progression, follow-up assessments will occur every 6 months and will include subsequent anti-neoplastic therapy and survival status of the patient until the follow-up period is terminated (see Reasons for Follow-up Termination). Physical exams, and all other assessments, are at the discretion of the treating physicians.

### Reasons for Follow-up Termination

Patients will remain in the follow-up period until any of the reasons below are satisfied:

- Completion of the study
- Patient death
- Patient withdraws consent from the follow-up period
- Patient is lost-to follow-up

### Termination of Follow-up

Patients whose follow-up period terminates should have the final date of contact recorded in the End of Study CRF in REDCap.

- For patients in follow-up at completion of the study, please use the study termination date
- Patients found to be deceased in the follow-up period should have their date of death recorded in the End of Study CRF.
- For patients who withdraw consent from follow-up, use the date the patient withdrew consent. Notify the Coordinating Center's data manager of the patient withdrawal of consent from follow-up, along with supporting documentation, should this occur.
- For patients who meet the criteria to be lost-to follow-up, enter the last date of known contact with the patient, along with comments in the CRF indicating the patient is lost-to follow-up.

### Lost-to Follow-up

All efforts should be made to assess the survival status of each patient until the follow-up period is terminated. A patient will be considered lost-to follow-up when 1) the patient is due for a follow-up contact as per the Table of Assessments, and 2) at least 2 attempts to contact the patient have occurred since the follow-up was due. Documentation of these 2 attempts should be sent to the Coordinating Center's data manager (see Registration and Data Handling).

## **Timing of assessments**

See Table of Assessments

Study Day a	PRE STUDY k	Cycle 1				Cycle 2				Cycle 3				Cycle 4				FU Prior to Progression c	Safety FU 30 days after last treatment dose	FU After Progression d
		W	W	W	W	W	W	W	W	W	W	W	W	W	W	W b				
REQUIRED STUDIES																				
PHYSICAL																				
History and Physical Exam e	X	X	X	X	X	X	X	X	X	X	X	X	X	X	X	X	X	X	X	
Weight and Performance Status e	X	X	X	X	X	X	X	X	X	X	X	X	X	X	X	X	X	X	X	
Blood Pressure e	X	X	X	X	X	X	X	X	X	X	X	X	X	X	X	X	X	X	X	
Disease Assessment	X																			
Toxicity Evaluation/Support e		X	X	X	X	X	X	X	X	X	X	X	X	X	X	X	X	X	X	
Comprehensive Geriatric Assessment f	X				X															
Pill count					X															
LABORATORYl																				
CBC/Differential	X	X	X	X	X	X	X	X	X	X	X	X	X	X	X	X	X	X 	X	
Comprehensive Metabolic Panel g	X	X	X	X	X	X	X	X	X	X	X	X	X	X	X	X	X	X 	X	
- Phosphorus	X	X	X	X	X	X	X	X	X	X	X	X	X	X	X	X	X	X 	X	
INR	X	X	X	X	X	X	X	X	X	X	X	X	X	X	X	X	X	X	X	
aPTT	X	X	X	X	X	X	X	X	X	X	X	X	X	X	X	X	X	X	X	
SCANS																				
CT/MRI of Chest h	X																		X	
CT/MRI of Abdomen and Pelvis h	X																		X	
TREATMENT																				
Regorafenib i		X	X	X	X	X	X	X	X	X	X	X	X	X	X	X	X	X	X	

- a Except for week 1 visit, there is a window of +/- 5 days for subsequent follow up visits.
- b Patients with stable disease and on protocol treatment beyond cycle 4 will be followed every 4 weeks until disease progression.
- c Patients off protocol treatment secondary to reasons other than progression will have physical exams performed at least every 3 months or earlier as clinically indicated until closure of the study. Frequency of radiographic studies will be determined by the treating physicians.
- d After disease progression subsequent anti-neoplastic therapy and survival status will be assessed every 6 months for the remainder of the study or until death.
- e Alternate weekly visits may be substituted with a home visit or phone call for BP check and symptom evaluation if it is not feasible for patients to attend clinic visits weekly.
- f Comprehensive geriatric assessment (CGA) will be performed at baseline, at 4 weeks, and then every 12 weeks during the study protocol (+/- 7 days). The baseline CGA can be performed at the week 1 visit prior to dispensing Regorafenib. These questionnaires can be completed at the study visit or given to the patient to take home, complete, and send back, or mailed to the patient to be completed prior to the next visit.
- g CMP to include Sodium (Na), Potassium (K), Chloride (Cl), Bicarbonate (HCO3), Blood Urea Nitrogen (BUN), Creatinine (Cr), Glucose, Calcium (Ca), Magnesium (Mg), Total Protein, Albumin, Alkaline Phosphatase, Total Bilirubin, Alanine Aminotransferase (ALT) and Aspartate Aminotransferase (AST).
- h Pre-study imaging must have been completed within 30 days prior to registration. Restaging imaging will be performed every 12 weeks (+/- 7 days) when patients are on protocol treatment until disease progression and is defined by Response Evaluation Criteria in Solid Tumors (RECIST 1.1)
- i Treatment will be given 3 weeks on/1 week off and will continue until disease progression or other reason for discontinuation of protocol treatment.
- j Lab work is required every 4 weeks after cycle 4 as long as patient remains on study
- k Initial screening period is 14 days from the date of consent. Once approved, by the coordinating site, an additional 14 day period is granted for scheduling, in which subjects must start treatment
- l Pre study labs can be used for week 1.

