## Clinical Experience

Two phase III global randomized studies have evaluated the efficacy of regorafenib. The CORRECT (Patients with metastatic colorectal cancer treated with regorafenib or placebo after failure of standard therapy) trial is an international, multicenter, randomized, double-blind, placebo-controlled study that enrolled 760 patients with mCRC whose disease had progressed after approved standard therapies. Metastatic colorectal cancer patients were randomized to regorafenib plus best supportive care (BSC) or placebo plus BSC. Treatment cycles consisted of 160 mg of regorafenib (or matching placebo) once daily for three weeks on / one week off plus BSC. The primary endpoint of this trial was overall survival. Secondary endpoints included

progression-free survival, objective tumor response rate and disease control rate. The safety and tolerability of the two treatment groups were also compared.

At a preplanned second interim analysis, there was a statistically significant survival benefit for regorafenib. The estimated hazard ratio for overall survival was 0.773 (95% confidence interval [CI], 0.635 to 0.941; 1-sided  $p = .0051$ ). Patients treated with regorafenib had a median overall survival of 6.4 months, compared with 5.0 months for placebo — a 29% increase in survival. In addition to improved overall survival, progression-free survival was superior; median progression-free survival was 1.9 months (95% CI, 1.88 to 2.17) for regorafenib and 1.7 months (95% CI, 1.68 to 1.74) for placebo. The estimated hazard ratio for progression-free survival was 0.493 (95% CI, 0.418 to 0.581; 1-sided  $p < .000001$ ). There was a substantial difference in disease control rate in the regorafenib and placebo groups (44% vs. 15%;  $p < .000001$ ).

Regorafenib demonstrated comparable efficacy benefits across patient subgroups analyzed including age, number of mets, number of lines of prior therapy, and kras status.

The most frequent grade 3+ adverse events in the regorafenib (versus placebo) group were hand-foot skin reaction (17%), fatigue (15%), diarrhea (8%), hyperbilirubinemia (8%), and hypertension (7%). The efficacy and safety results from the CORRECT study supported FDA approval in September 2012.

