## 4. Study Design

Given 54% grade 3/4 toxicity and required dose modification among 76% of patients in the regorafenib arm (randomized phase III CORRECT trial), we will initiate treatment at a reduced dose of 120mg in this geriatric study population on a similar 3 weeks on/1 week off schedule. Dose escalation to 160mg will be recommended after the first cycle (4 weeks) at the discretion of the treating physician. There is good precedent for starting at reduced doses in similar trials – the FOCUS2 study team utilized 80% starting chemotherapy doses in their study among the elderly with metastatic CRC and dose escalated if tolerated.

Participants will undergo a comprehensive geriatric assessment (CGA) at baseline, at 4 weeks and then every 3 months (+/- 7 days) while on study to assess for any deterioration in geriatric domains (functional status, comorbidities, nutrition, psychological state, social support and cognitive ability). All sites have personnel experienced in performing geriatric assessments and the University of Rochester as the lead site will conduct training to ensure that all sites will conduct the assessments in the same way.

All patients will receive intensive one-on-one education about prevention/management of skin toxicity, diarrhea, fatigue and other toxicities at initiation and follow-up visits (see section 7 & 8 for review of treatment strategies). Starter packs with moisturizing cream (10% urea content), socks and patient-friendly ‘Tips for Skin Care’ will be distributed. On-treatment visits will occur weekly for first two cycles and every 4 weeks after that. Alternate weekly visits may be substituted with a home nursing visit for BP check and symptom evaluation if it is not feasible for patient to attend clinic visits weekly. Pill adherence diaries will be provided to patients and pill counts will be performed at the end of every cycle.

Restaging CT/MRI scans will be completed every 12 weeks (+/- 7 days) (or sooner if treating oncologists suspects progression of disease based on clinical symptoms). Radiographic disease progression is defined by Response Evaluation Criteria in Solid Tumors (RECIST 1.1) (see Appendix A). Subjects will have a Safety Follow-up visit within 30 days after their last dose of study drug or prior to the initiation of another antineoplastic therapy, whichever occurs first. After treatment discontinuation, survival status will be assessed periodically (see Table of Assessments).

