## **7. Treatment[s]**

### **Treatments to be administered**

All patients will receive regorafenib 120mg daily for 3 weeks on and 1 week off with cycle 1. Dose escalation to 160mg will be permitted after the first cycle at the discretion of the treating physician. Subjects will continue study treatment until disease progression or other reasons for removal from treatment (section6).

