**Hypertension**

Hypertension is a known AE associated with regorafenib treatment. Subject will have their blood pressure measured weekly during the first 8 weeks of treatment (either in the office or with nursing services).

If additional blood pressure measurements are done outside the study site, and the blood pressure is > 140 mm Hg systolic or > 90 mm Hg diastolic (NCI CTCAE v4.0), then the subject must contact study personnel.

The management of hypertension, including the choice of antihypertensive medication, will be performed according to local standards and to the usual practice of the investigator. Every effort should be made to control blood pressure by medical means other than study drug dose modification. If necessary, Table 8-4 outlines suggested dose reductions.

Table 8-3: Management of Treatment-Emergent Hypertension		
Grade (CTCAE v4.0)	Antihypertensive Therapy	Regorafenib Dosing

1
 
Prehypertension (systolic BP 120 - 139 mmHg or diastolic BP 80 - 89 mmHg)
	None	
 
• Continue regorafenib
 
• Consider increasing blood pressure (BP) monitoring
 

2
 
Systolic BP 140 - 159 mmHg or diastolic BP 90 - 99 mmHg, OR Symptomatic increase by > 20 mmHg (diastolic) if previously within normal limits
	
 
• Treat with the aim to achieve diastolic BP ≤ 90 mm Hg:
 
• If BP previously within normal limits, start anti-hypertensive monotherapy
 
• If patient already on anti-hypertensive medication, titrate up the dose.
 
	
 
• Continue regorafenib
 
• If symptomatic, hold regorafenib until symptoms resolve AND diastolic BP ≤ 90 mm Hga. When regorafenib is restarted, continue at the same dose level.
 

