
3
 
Systolic BP ≥ 160 mmHg or diastolic BP ≥ 100 mmHg OR More than one drug or more intensive therapy than previously used indicated
	
Treat with the aim to achieve diastolic BP ≤ 90 mm Hg: Start anti-hypertensive medication
 
AND/OR Increase current anti-hypertensive medication
 
AND/OR Add additional anti-hypertensive medications.
	
 
• Hold regorafenib until diastolic BP ≤ 90 mm Hg, and if symptomatic, until symptoms resolve.a
 
• When regorafenib is restarted, continue at the same dose level.
 
• If BP is not controlled with the addition of new or more intensive therapy, reduce by 1 dose level.b
 
• If Grade 3 hypertension recurs despite dose reduction and antihypertensive therapy, reduce another dose level.c
 

4
 
Life-threatening consequences (eg, malignant hypertension, transient or permanent neurologic deficit, hypertensive crisis)
	Per institutional guidelines	Discontinue therapy

a. Patients requiring a delay of >4 weeks should go off protocol therapy
 
b. If BP remains controlled for at least one cycle, dose re-escalation permitted per investigator's discretion.
 
c. Patients requiring >2 dose reductions should go off protocol therapy.
		

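### Table of Assessments footnote e lets a phone call stand in for the alternate-week blood pressure check, which Sections 4 and 8 do not allow

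*Combined protocol and SAP*

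**What the plan says.** Three current provisions govern the same weekly check.

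- **Section 8, Hypertension:** "Subject will have their blood pressure measured weekly during the first 8 weeks of treatment (either in the office or with nursing services".
- **Section 4, Study Design:** "Alternate weekly visits may be substituted with a home nursing visit for BP check and symptom evaluation", if the patient cannot feasibly attend weekly.
- **Section 10, Table of Assessments, footnote e:** "Alternate weekly visits may be substituted with a home visit or phone call for BP check and symptom evaluation", under the same condition. The footnote is attached to the history and physical, weight and performance status, blood pressure, and toxicity rows. The laboratory rows do not carry it.

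Two further provisions depend on the readings. For Grade 3 hypertension, Table 8-3 says: "Hold regorafenib until diastolic BP ≤ 90 mm Hg, and if symptomatic, until symptoms resolve". Section 7 says: "Dose escalation to 160mg will be permitted after the first cycle at the discretion of the treating physician".

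**The concern.** The Section 4 sentence and footnote e are almost the same, but the footnote drops the word nursing and adds the phone call. Staff usually schedule visits from the assessment table, so footnote e is the version most likely to be followed. A site relying on it and a site relying on Section 8 would each believe it was compliant, while collecting different data.

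What is at stake is safety monitoring. Table 8-3 grades and manages hypertension on measured pressure: Grade 3 starts at 160 mmHg systolic or 100 mmHg diastolic. A symptom review by phone cannot find an asymptomatic rise. The first two cycles are when weekly readings are required, and they include the point at which escalation from 120 mg to 160 mg is first allowed.

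**Working it through.** The plan states no figure on this point, so there is none to reproduce. The check compares the provisions and then counts visits.

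**1. Do the provisions agree?**

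| Provision | Accepted ways to do the alternate-week check |
|---|---|
| Section 8, Hypertension | Office, or nursing services |
| Section 4 | Clinic visit, or home nursing visit |
| Footnote e | Clinic visit, home visit (staff type not stated), or phone call |

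Sections 4 and 8 are compatible. Footnote e permits a route that neither of them allows.

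**2. How many readings can be affected?**

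Inputs: visits are weekly for two cycles (Section 4), a cycle is 28 days (Section 7), and Section 8 asks for weekly readings over 8 weeks. That gives 2 × 28 / 7 = 8 readings. I assume that week 1 is in clinic and that *alternate* means no two consecutive weeks are substituted.

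- Nominal days for weeks 1 to 8: 1, 8, 15, 22, 29, 36, 43, 50.
- The largest set of non-consecutive weeks from 2 to 8 is weeks 2, 4, 6 and 8, so 4 are substituted.
- Staff-measured readings then fall on days 1, 15, 29 and 43: 8 − 4 = 4 of 8, nominally 14 days apart.

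**3. If week 4 is held in clinic**

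The weeks left are 2–3 and 5–8. At most one can be substituted from the first group and two from the second, so 1 + 2 = 3 of 8. The maximum stays at 3 if week 8 is also in clinic (for example weeks 2, 5 and 7).

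**4. What this means for dosing decisions**

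With calls in weeks 2, 4, 6 and 8, the first staff reading after starting drug is nominally day 15 of the 21 dosing days in cycle 1. It is also the only one between the first dose and the week 5 visit on day 29, when escalation can first occur. The next staff reading after that is day 43, which is 43 − 29 = 14 days later. If week 4 is in clinic, there are two staff readings in that interval instead of one.

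**The case against.** The strongest reply is that nothing is necessarily lost. Footnote e names the blood pressure check as a purpose of the call, so a patient with a cuff could read out a value. The footnote is permissive, applies only where weekly attendance is not feasible, and does not expressly waive the weekly measurement in Section 8. This stands in part. A reader might infer that half of the readings would simply be missing, and the documents do not support that. What footnote e puts at risk is the office or nursing measurement. Whether a home value replaces it depends on equipment that the protocol neither supplies nor requires.

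A reader might also infer that Section 8 demotes every off-site reading to an extra, because it says: "If additional blood pressure measurements are done outside the study site". That is too strong. Home nursing readings are also taken off site, and they count. The sentence sets a threshold for contacting study staff; it does not settle whether a value given by phone meets the weekly requirement.

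Finally, week 4 is likely to be in person. Section 4 calls for a pill count at the end of each cycle and a geriatric assessment at 4 weeks, and that assessment includes a physical performance test. This is why the 3-of-8 figure is given, although the text does not expressly require the week 4 visit to be in clinic. Weekly blood draws may also bring patients in, but nothing requires a blood pressure reading at a draw.

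**Conclusion.** The inconsistency is real and worth correcting. Its size is at most 4 of 8 required readings without an office or nursing measurement, or 3 of 8 if week 4 is in clinic. This holds only for patients who cannot attend weekly and whose site uses calls at every opportunity. It rests on the two assumptions stated in the working. The documents do not say how many patients would be in this position.

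Three stronger readings are tempting but not supported:

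- **Patient count.** A reader might multiply the 7% rate of grade 3+ hypertension quoted from CORRECT by 60 patients. That rate comes from a 160 mg starting dose. It is not limited to the first 8 weeks, to patients using calls, or to events a nurse would have found earlier, so the product does not measure this defect.
- **Primary endpoint.** A reader might infer that grade 3–5 toxicity would be undercounted. The documents give no basis for saying by how much, or that it would happen at all, and no such effect is claimed.
- **Visit window.** A reader might see a second fault in footnote a: "Except for week 1 visit, there is a window of +/- 5 days for subsequent follow up visits". A wide window on weekly visits contradicts no other rule. The two-weekly liver-test minimum in Section 10 is set separately and still binds. Narrowing the window would be a preference.

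This is a minor consistency correction to safety monitoring.

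**What to change.** In footnote e, replace *home visit or phone call* with *home nursing visit*, to match Section 4. Alternatively, keep the call for symptom review only, on condition that blood pressure is measured that week in the office or by nursing services.

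The cost is an edit to one footnote and up to 4 nursing visits in place of calls for each patient who cannot attend weekly. No new procedure is needed, because Sections 4 and 8 already provide for nursing visits. With either wording, all 8 weekly readings are staff-measured.
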